3. We will determine whether supervised exercise therapy alone (Group C) is associated with significantly greater increases in CD34+ cells and other progenitor cell measures at two-week follow-up, six-week follow-up and at six-month follow-up, compared to Group D.
4. Among participants receiving GM-CSF, we will determine whether the degree of increase in progenitor cell measures at two-week follow-up is associated with the degree of improvement in remaining study outcomes at six-week, 12-week, and six-month follow-up, respectively.
5. Among up to 30 participants with PAD and 15 consenting participants who are determined not to have PAD, we will determine whether progenitor cell measures increase acutely after a treadmill exercise stress test among participants with PAD and among those without PAD, respectively. We will further determine whether greater increases in progenitor cell measures after a treadmill exercise stress test are associated with better six-minute walk performance and higher ABI values at baseline, compared to lesser increases in progenitor cell measures after a treadmill exercise stress test.

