B2. Distinctive features of this trial as compared to prior work. We are aware of one ongoing randomized clinical trial comparing the ability of GM-CSF vs. placebo to improve walking performance in patients with PAD (NCT number NCT0104141). Our proposal has many unique features as compared to this ongoing study. First, our proposal will test whether the combination of GM-CSF and supervised treadmill exercise is superior to GM-CSF alone and supervised treadmill exercise alone, respectively, for improving functional performance in PAD. Preliminary data support our hypothesis that GM-CSF may be most efficacious when delivered with supervised treadmill exercise, but this question is not being addressed by any study to our knowledge. Second, by measuring outcomes at six-weeks, 12-weeks, and six-month follow-up, our proposal will assess the temporal trajectory of favorable changes in response to GM-CSF with and without exercise therapy. Third, our proposal includes PAD participants both with and without classical intermittent claudication symptoms. This is important because most PAD patients do not have classic intermittent claudication symptoms. Asymptomatic PAD patients and PAD patients with atypical symptoms have significant functional impairment and faster functional decline than people without PAD (6,7,51). Fourth, whether supervised treadmill exercise, at the frequency and duration recommended by clinical practice guidelines (35), increases CD34+ cells in PAD participants is unknown. Our proposal will help establish whether increases in CD34+ cells mediate the favorable effects of supervised treadmill exercise in PAD. Fifth, we will use the six-minute walk test as our primary outcome measure. Our data and that of others demonstrate that the six-minute walk test is a better measure of community walking ability than treadmill testing in patients with PAD (see Section C12) (52-54).

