C1d. Additional evidence of our expertise with progenitor cells and PAD. [name] recently completed a randomized controlled trial of 28 PAD participants with critical limb ischemia who were randomized to either a control group vs. CD34+ cell mobilization, apheresis, and re-injection of CD34+ cells into calf muscle. At six-month follow-up, amputation-free survival was significantly higher among those receiving CD34+ cell calf injections as compared to the control group (hazard ratio =0.26, p=0.016). This study provides additional evidence of our expertise and the benefits of CD34+ cells for patients with PAD.

Preliminary Data Summary. Our prior work has established that people with PAD, both with and without intermittent claudication symptoms, have greater functional impairment and faster rates of functional decline compared to those without PAD (6-8,51,55-57). Our SILC randomized trial of exercise demonstrated that a supervised treadmill walking exercise intervention significantly improves walking performance and brachial artery flow-mediated dilation in PAD participants both with and without symptoms of intermittent claudication (44). Our pilot data demonstrate that higher concentrations of CD34+ cells are associated with better walking performance in PAD. Our preliminary work demonstrates the validity, reliability, and feasibility of our methods.

C2. STUDY OVERVIEW. The PROPEL study design is a randomized controlled clinical trial of 240 participants with PAD who will be randomized to one of four study arms in a 2 x 2 factorial design: Group A: GM-CSF and supervised treadmill exercise; Group B: GM-CSF and attention control condition; Group C: placebo injections and supervised treadmill exercise; Group D: placebo injections and attention control condition (Figure 2). Potentially eligible participants will be required to successfully complete a two-week combined exercise/attention control run-in period prior to randomization. The run-in will help identify potential participants unlikely to adhere to study requirements (58).

[figure not shown]

Table 5 summarizes characteristics of the four study intervention groups.

Table 5. Four Study Arms

Supervised Treadmill Exercise		Attention Control Condition
GM-CSF	Group A. GM-CSF injections x 2 weeks + Supervised treadmill exercise x 6 months	Group B. GM-CSF injections x 2 weeks + Attention control condition x 6 months.

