For our Exploratory Aims, we will use linear mixed effects regression analyses to compare changes in six-minute walk performance, maximal treadmill walking time, and brachial artery FMD between baseline and six-week follow-up and between baseline and six month follow-up between Groups A and B, Groups A and C, Groups B and D, and Groups C and D. We will use linear mixed effects regression analyses to compare changes in progenitor cell measures between baseline and six-week follow-up and between baseline and six-month follow-up between Groups C and D. Outcomes measured at baseline and each follow-up visit will be longitudinal response variables in the regression model. The regression coefficients for the interactions between group indicators and visit time are parameters of interest. The subject specific random intercept will be used to incorporate the within subject correlations. For our Exploratory Aim #4, we will employ linear mixed regression analysis to evaluate the association between changes in CD34+ cells and other progenitor cell measures from baseline to two-week follow-up with changes in six-minute walk distance, brachial artery FMD, and maximal treadmill walking time between baseline and six-week, twelve-week, and six-month follow-up visits. The responses are longitudinally measured outcomes of change between baseline and the six-week, twelve-week, and six-month visits, respectively. The independent variables of interest are changes in CD34+ cells and other progenitor cell measures from baseline to two-week follow-up. We will employ similar linear mixed regression analysis to evaluate associations between changes in progenitor cells between baseline and six-week, 12-week, and six-month follow-up with changes in six-minute walk distance, brachial artery FMD, and maximal treadmill walking time during the corresponding time period. The responses are longitudinally measured outcomes of change between baseline and the six-week, twelve-week, and six-month visits, respectively. Independent variables of interest are changes in progenitor cells from baseline to six-week, 12-week, and six-month follow-up. Finally, we will perform regression analyses among participants randomized to

the exercise group to determine whether the degree of increase in lactate levels during exercise sessions is associated with the degree of increase in progenitor cells.

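### The progenitor-cell association models name no term for randomised assignment, so a model fitted as written mixes the within-arm association with the effects of exercise (and possibly GM-CSF)

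*Combined protocol and SAP*

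**What the plan says.** Exploratory Specific Aim 4 sets the population of the two-week model: "Among participants receiving GM-CSF, we will determine whether the degree of increase in progenitor cell measures at two-week follow-up is associated" with later improvement in the other outcomes. Section C2 defines the two arms that receive GM-CSF: "Group A: GM-CSF and supervised treadmill exercise; Group B: GM-CSF and attention control condition". Exercise assignment therefore varies within the Aim 4 population, while GM-CSF assignment does not.

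C21 names the predictors of that model: "The independent variables of interest are changes in CD34+ cells and other progenitor cell measures from baseline to two-week follow-up". It then adds a second analysis: "We will employ similar linear mixed regression analysis to evaluate associations between changes in progenitor cells between baseline and six-week, 12-week, and six-month follow-up", with outcome changes over the same periods as responses. For this one, "Independent variables of interest are changes in progenitor cells from baseline to six-week, 12-week, and six-month follow-up". No population is given.

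Group terms do appear in C21, but for the between-group comparisons: "The regression coefficients for the interactions between group indicators and visit time are parameters of interest". The covariate rule at the start of C21 concerns baseline characteristics that turn out to differ between groups; randomised assignment is not one of these. The lactate regression that closes the exploratory paragraph is restricted to participants randomised to exercise, so C21 does set a population by arm in places.

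**The concern.** Exercise is hypothesised to improve the six-minute walk (Primary Aim, items 1 and 3) and to raise CD34+ cells (Secondary Aim 3, Exploratory Aim 3 and section A7). If both are true, exercise assignment is a common cause of predictor and response. Exercisers in Group A would tend to have larger values of both, non-exercisers in Group B smaller values of both, and the pooled regression would slope upwards even if cell change says nothing about walking within either arm.

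If the second model pools all four arms, GM-CSF assignment acts in the same way. It is expected to raise CD34+ cells (A5) and hypothesised to improve walking (Primary Aim, item 2). Should it raise cells without affecting walking, it would instead dilute the pooled slope.

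At stake is the reading of the dose-response question. D3 lists it among the things the trial is needed to establish, and B3 says that an association would steer future studies towards maximising CD34+ levels.

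**Working it through.** The documents give no effect size, power or error rate for the association models, so there is no stated figure to reproduce. What follows is an illustration of size.

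**1. Effect of exercise on walking.** Table 2 (prior exercise trial, six months) gives +21.28 m with treadmill exercise (n=50) and -15.02 m in controls (n=47), p<0.001.
- Difference: 21.28 + 15.02 = 36.3 m.
- If the p-value came from an unadjusted t-test (assumed; Table 2 does not name the test), t(95 df) at two-sided p=0.001 is 3.396, so SE is at most 36.3/3.396 = 10.69 m.
- SD of change is at most 10.69/sqrt(1/50 + 1/47) = 10.69/0.2032 = 52.6 m.
- Standardised effect dy is at least 36.3/52.6 = 0.69.

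**2. Effect of exercise on CD34+ change (dx).** The documents give no size. I assume 0.3 to 0.8 within-arm SD.

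**3. Correlation induced by pooling two equal arms with no within-arm association.**

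r = (dx·dy/4) / sqrt[(1 + dx²/4)(1 + dy²/4)]

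For dx=0.5 and dy=0.69: 0.08625 / sqrt(1.0625 × 1.1190) = 0.079.

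**4. False-positive rate at two-sided 5%,** by Fisher's z, one outcome visit at a time. The final sample is 210 (C20), so about 105 received GM-CSF. The last column takes all four arms with no effect of GM-CSF on cells or walking.

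| dx (assumed) | induced r | A+B, n=105 | all arms, n=210 |
|---|---|---|---|
| 0 | 0 | 5% | 5% |
| 0.3 | 0.048 | 8% | 11% |
| 0.5 | 0.079 | 13% | 21% |
| 0.8 | 0.121 | 23% | 42% |

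**5. Check by simulation** (10,000 trials per scenario, 52 per arm, SD 52 m so dy=0.70).
- A+B without an arm term: 7%, 13% and 24% at dx = 0.25, 0.5 and 0.8.
- The same at alpha 0.0125 (C22): 2%, 5% and 11%.
- A+B with an arm term, same shifts: 4.7% to 5.1% at nominal 5%, and mean partial correlation about 0.
- All four arms, when GM-CSF adds 1 SD to CD34+ change but nothing to walking: 8%, 18% and 36%, against 9%, 21% and 43% when it adds nothing to either.

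**6. Sensitivity to the walking effect,** A+B at nominal 5%, dx = 0.25, 0.5 and 0.8.
- SD 72.6 m (dy=0.50): 6%, 9% and 15%.
- SD 36.3 m (dy=1.00): 9%, 20% and 39%.

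**The case against.** **The plan is silent; it does not exclude an arm term.** C21 lists variables of interest, which names target coefficients and need not be the full covariate list. A reader might infer that the sponsor has decided against adjustment. The text does not support that. What stands is that no rule in the plan supplies the term, and an analyst following C21 literally would leave it out.

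**At two weeks the shift may be close to zero.** By then exercise has barely begun: three sessions a week, starting at 15 minutes (C7), with none on the day of the first injection (D2). Everyone in A and B is also receiving a drug that mobilises CD34+ cells. The cited evidence in PAD is mixed even after four weeks of much more frequent walking (A8). This objection holds, and it moves the weight of the point to the concurrent 12-week and six-month models.

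**The sizes are borrowed.** The walking effect is a six-month figure and may be smaller at six or 12 weeks. It does not carry over to FMD, where Table 2 gives p=0.02. Most A+B analyses in the illustration (77% to 92%) would show no nominally significant result. At 0.0125 the rate is about 2% to 11%, although the plan does not say whether that level applies to exploratory models.

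**Intended use.** A reader might infer that the plan will present these slopes as proof that cells drive the walking benefit. The aims and D3 speak only of association. B2 does say "Our proposal will help establish whether increases in CD34+ cells mediate the favorable effects of supervised treadmill exercise in PAD", but that sentence follows the question of whether exercise raises CD34+ cells, which is the randomised comparison of Groups C and D. B3 also reasons from arm-level patterns. That is a partial safeguard for interpretation, but it does not adjust the regressions.

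**Conclusion.** The concern holds as a gap in the specification of exploratory analyses. As written, both association models combine the within-arm relation with the effect of assignment, and the second also leaves its population open. The resulting error could be material at 12 weeks and six months and may be negligible at two weeks.

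The illustrated rates of 8% to 23% (A and B) and 11% to 42% (all 210) rest on three assumptions: a walking effect near 0.69 SD, a CD34+ shift of 0.3 to 0.8 SD that no document supports with a figure, and no within-arm association. If exercise does not move CD34+ cells, exercise assignment causes no inflation. The four primary tests and the randomised secondary comparisons are untouched.

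**What to change.** In C21:
- State the population of the second association model, and repeat there that the Aim 4 model is limited to GM-CSF recipients.
- Include randomised exercise assignment as a fixed effect, with its interaction with visit. Where all arms are used, also include GM-CSF assignment and the exercise-by-GM-CSF interaction, each with visit.
- Report the assignment-adjusted slope as the result, described as an association. Adjustment removes confounding by assignment only; adherence or general health could still link cells to walking, so the slope would not establish mediation.

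The cost is a few sentences and no new data. With three follow-up visits, A and B need about three extra parameters (one assignment term at each visit). All arms need about nine (three assignment terms at each of three visits). Precision falls slightly. C20 already revises the analysis plan before the data are analysed, and this change could be part of that revision.
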